b. Variable Transformations: Transformations will be employed as needed to produce variables that conform to the distributional assumptions underlying the regression models that will be used. For example, some variables may be transformed to the logarithm scale for analysis, to reduce any marked positive skew; in these cases, results will be reported on the original scale of the variable to aid in interpretation.

Transformations may also be required to ensure additivity of variable effects in general linear models (for example, the outcome may be a quadratic rather than a linear function of age).

Stage 3 – Inferential Analysis:

Specific Aim 1: Compare the outcomes of surgery and non-operative treatment in patients aged 40 to 80 with ASLS defined as a lumbar curve with a coronal Cobb measurement $\geq 30^\circ$ and either of the following: Oswestry (ODI) score of 20 or more, or Scoliosis Research Society Quality of Life instrument (SRS-QOL) score of 4.0 or less in the domains of pain, function and/or appearance.

a. Primary Analyses: All the data analyses required to fulfill the specific aims of the study will be accomplished using statistical methods for repeated measures and longitudinal data using the SAS system's MIXED and GLIMMIX procedures for continuous and categorical outcomes, respectively. These procedures use maximum likelihood methods to estimate variances associated with the fixed and random effects of the model. In the randomized cohort, the primary analysis will be on an intent-to-treat basis. For the observational cohort, differences between treatment groups are expected at baseline and these will be controlled for by using covariate adjustment within the longitudinal regression models. We will model each HRQOL measure as the change at follow-up from baseline at each study month (i.e., at 3, 6, 12, 18, 24, 30, 36, 42, and 48 months), adjusting for baseline level while clustering the vector of outcomes within patients. Results will provide estimated means and standard deviations for the rate of change over the 12-month and 24-month (primary endpoint) follow-up periods, (1) assuming a linear rate of change, and (2) not assuming linearity. We will also report the 3-year and 3-year changes (and 95% confidence intervals) predicted by these models. For SRS-QOL and SF-12, component domains will be analyzed both combined and separately as described by Mangione et al.

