Evaluating the statistical power for a mixed model longitudinal analysis is not straightforward. One conservative approach is to power the study with regard to a simple effects test associated with the highest order effect of interest in the study, here the Treatment x Assessment Time interaction. In this case, the sample size for the two treatment groups is estimated and, since the two treatment groups are not matched, the sample size per treatment group is likely to be larger than would be required to establish a significant change in outcome within a Treatment group across Assessment Time simple effects test (e.g., difference in SRS scores from baseline to 2-year follow-up). Accordingly, this study was powered with respect to the simple effects tests associated with a significant Treatment x Assessment Time interaction at the primary 2-year endpoint. This power analysis is informed by the data already gathered by the SDRG with the mean and standard error estimated adjusted for SRS baseline and patient age gender and Cobb angle. **Table 2 summarizes estimated sample sizes per treatment needed to achieve power of .80 for 2-tailed testing with type I error rate set at .05 under a variety of effect sizes, based on mean and standard deviation estimates.** The two rows highlighted were judged to reflect the most likely scenarios and, overall, the sample size of 30 per group in the RCT was considered a reasonable choice for achieving sufficient power to detect a real difference between the two treatment groups at 2-years follow-up.

Table 2

Estimated Means		Common SD	Effect Size	N per Group
Trt 1	Trt 2			
0.3	0.8	0.6	0.833	24
0.4	0.8	0.6	0.667	37
0.5	0.8	0.6	0.500	64
0.3	0.8	0.7	0.714	32
0.4	0.8	0.7	0.571	50
0.5	0.8	0.7	0.429	87

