Treadmill evaluation. Again, longitudinal mixed model regression analysis will be used to evaluate the treadmill evaluation. However, since crossover to surgery will trigger a “new” baseline treadmill test, these patients will be repeated in the analysis with their 2nd baseline considered their follow-up treadmill test relative to the 1st baseline score and their final treadmill test 2 years following their 2nd baseline treadmill test will be considered their follow-up treadmill test relative to their 2nd baseline treadmill test.

Treadmill = treatment | interval| time site age sex

Treadmill = treatment | T_DOI(interval) site age sex

Patients who crossed over to surgery will be provided with a second DOI value (DOI_cNS) that will be used in conjunction with the date of the follow-up treadmill test to define the delta associated with the 2 year interval data form used to gather the follow-up treadmill score.

Addendum 1/17/13: Sample Size Calculation.

A sample size of 82 patients (41 per treatment arm) was estimated to provide 80% power with an SRS-22 effect size of ≥ 0.714 , 10% loss-to-follow-up at 2 years postoperative, and 20% crossover from nonoperative to operative intervention, based upon a mixed-model longitudinal analysis accounting for repeated measures at follow-up. A priori sample size estimations require estimates of outcome variances that may be inaccurate in the actual population studied. To account for this a bootstrap sample size estimation using data from the first 26 patients randomized was performed to provide a more accurate assessment of the required sample size needed to address the original trial aims, to include both the SRS-QOL and ODI.

Sample Size Estimation

Interval	ODI Power	SRS Power	n/GRP
3 months	0.0390	0.6770	18
6 months	0.7270	0.9980	
9 months	0.5600	1.0000	
12 months	0.8170	0.9950	

These results suggested that >80% power could be achieved to address Aim #1 with 36 randomized patients (18 patients per group).

Enrollment in the Observational cohort closed May 2013. Enrollment in the randomized cohort closed July 2014 with 63 participants, 70% of the original enrollment goal, this enrollment goal was felt, based on the above sample size analyses, to allow for sufficient power making allowances for loss to follow-up and cross-over over time.

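### The SAP's claim of over 80% power with 36 patients, and of sufficient power with 63, rests on a bootstrap table that stops at 12 months, so 80% power at the 24-month primary endpoint is not demonstrated

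*SAP*

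**What the plan says.** **Primary time point.** SAP 1.6.1 (Stage 3, Primary Analyses) refers to the "24-month (primary endpoint) follow-up periods". SAP 1.6.2 says the study was powered on the simple effects tests for the treatment-by-time "interaction at the primary 2-year endpoint". Protocol 1.5.1 names change in the SRS-QOL subscore as the primary outcome.

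**Planning figures.** SAP 1.6.2 and 1.6.4 give 32 to 37 patients per group for 80% power, two-sided 0.05. In Table 2 these are the rows with effect sizes 0.714 and 0.667. SAP 1.6.2 adds that "the sample size of 30 per group in the RCT was considered a reasonable choice for achieving sufficient power". SAP 1.6.3 expects 82 randomised, 10% loss by 2 years and 20% crossover from the non-operative arm.

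**Re-estimation.** In the addendum of 1/17/13, "a bootstrap sample size estimation using data from the first 26 patients randomized was performed" for both SRS-QOL and ODI. Its table shows:

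| Interval | ODI power | SRS power |
|---|---|---|
| 3 months | 0.039 | 0.677 |
| 6 months | 0.727 | 0.998 |
| 9 months | 0.560 | 1.000 |
| 12 months | 0.817 | 0.995 |

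The conclusion drawn is: "These results suggested that >80% power could be achieved to address Aim #1 with 36 randomized patients (18 patients per group").

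**Closure.** "Enrollment in the randomized cohort closed July 2014 with 63 participants, 70% of the original enrollment goal"; on the strength of the analyses just described, that number was felt "to allow for sufficient power making allowances for loss to follow-up and cross-over over time".

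**The concern.** The addendum makes a general statement about Aim 1 and then a sufficiency statement about 63 patients, yet its table has nothing beyond 12 months. The other calculation in the addendum is the restated design for 82 patients, which cannot support a smaller number. The bootstrap therefore carries the whole argument for 63, and it does not reach the endpoint the trial was powered on. Nor does the SAP show how loss and crossover were allowed for in reaching 63.

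At stake is how the 2-year intent-to-treat result will be read. If it is null, a reader who trusts the addendum will take it as coming from a comparison with more than 80% power. The SAP's own planning inputs do not give that for 63 patients at 24 months.

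**Working it through.** **Method.** Two-sample t-test, two-sided alpha 0.05. With d the effect size, the non-centrality is d × √(n₁n₂/(n₁+n₂)) on n₁+n₂−2 degrees of freedom, and power comes from the noncentral t.

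**Step 1: reproduce the SAP's figures.** For the six Table 2 rows (24, 37, 64, 32, 50 and 87 per group) the method gives power of 0.807, 0.808, 0.801, 0.803, 0.808 and 0.803. For the 29 per group that SAP 1.6.4 quotes for 70% power at 0.667 it gives 0.704. It is therefore a fair yardstick for the SAP's planning.

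**Step 2: read the bootstrap table on its own terms.** ODI passes 0.80 only at 12 months. SRS falls short at 3 months and is at least 0.995 from 6 months. Both pass only at 12 months. There is no 24-month row.

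**Step 3: 18 per group at the planning effects.** √(18×18/36) = 3, so the non-centrality is 2.00 at d = 0.667 and 2.14 at d = 0.714. Power is 0.493 and 0.549. Reaching 80% at this size needs d of about 0.96, above Table 2's largest value of 0.833. The bootstrap's figure cannot be reproduced, because the addendum gives no effect, SD or model for it.

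**Step 4: 63 patients at 24 months.** With 1:1 allocation, 63 gives 31 v 32. After the SAP's 10% loss, 63 × 0.9 = 56.7, taken as 28 v 29. For the original design, 41 × 0.9 = 36.9, taken as 37 v 37.

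The last two columns assume that crossover shrinks the intent-to-treat effect to 0.9 or 0.8 of plan. These factors are assumptions, not SAP figures. The 0.8 corresponds to 20% of the non-operative arm having surgery and gaining its full benefit by 24 months: the difference becomes μ₁ − (0.8μ₂ + 0.2μ₁) = 0.8(μ₁ − μ₂). Each cell gives power at d = 0.667 to 0.714.

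| Group sizes | No dilution | × 0.9 | × 0.8 |
|---|---|---|---|
| 31 v 32 (63, before loss) | 0.74–0.80 | 0.65–0.71 | 0.55–0.61 |
| 28 v 29 (63, after 10% loss) | 0.70–0.75 | 0.60–0.66 | 0.51–0.56 |
| 37 v 37 (82, after 10% loss) | 0.81–0.86 | 0.72–0.78 | 0.62–0.68 |

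The post-loss row counts lost patients as contributing nothing. SAP 1.6.3 keeps their earlier visits in the model, so the first two rows bracket the effect of loss. For reference, 30 per group gives 0.72 to 0.78 with no dilution.

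**Step 5: precision.** The expected 95% confidence interval half-width is t₀.₉₇₅,₅₅ × SD × √(1/28 + 1/29). It is 0.32 SRS points at SD 0.6 and 0.37 at SD 0.7, the two Table 2 values.

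**Step 6: the enrolment percentage and 0.814.** 63/82 = 77%. A figure of 70% implies a goal of 63/0.70 = 90, which neither document states; SAP 1.6.4 mentions about 100 (63%). Separately, SAP 1.6.3 cites effect sizes of 0.714 and 0.814 from Table 2. Table 2 has no 0.814, and the 32 to 37 per group in 1.6.2 and 1.6.4 match its 0.714 and 0.667 rows.

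**The case against.** **The SAP does not confine itself to 24 months.** Sections 1.6 and 1.6.2 also describe the sample size as serving a comparison at any chosen follow-up interval. The 8/29/12 addendum puts the primary hypothesis at each interval and plans p-values at 12 and 24 months. Aim 1 names no time point. This stands in part: 12-month power does bear on Aim 1. It does not supply power at the endpoint that 1.6.1 labels primary and 1.6.2 says was powered.

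**63 clears the SAP's own lower marks.** It exceeds the 30 per group in 1.6.2 at entry, and post-loss power of 0.70 to 0.75 is about the 70% level used in 1.6.4, where the target is 58 patients. This stands against calling 63 inadequate. But 70% was adopted there for futility purposes, whereas the addendum's claim is above 80%.

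**The t-test ignores covariate gain.** The planned model adjusts for baseline. If Table 2's SDs are unadjusted, as 1.6 implies, then at 28 v 29, where 80% power needs d = 0.756, a baseline correlation of √(1 − (0.667/0.756)²) = 0.47, or 0.33 for d = 0.714, would restore 80% before any crossover dilution. But 1.6.2 says those inputs were already "mean and standard error estimated adjusted for SRS baseline and patient age gender and Cobb angle". The gain is possible but cannot be counted on from the text.

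**The bootstrap was meant to replace inaccurate inputs.** The addendum's motive was that the planning variances might be wrong, so low power at the old inputs does not refute it. That stands. A reader might infer from Step 3 that the bootstrap is wrong, or convert its SRS powers into an observed effect and call that effect inflated. The documents support neither: the model and inputs are not reported, and a power figure passed backwards through an unadjusted t-test is not an observed effect.

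**Crossover would have weakened 82 patients too.** True, and the table in Step 4 applies the same factors to both sizes. Most of the fall below 80% in the diluted columns comes from the assumed dilution, not from stopping at 63.

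**Conclusion.** The point holds as a gap between claim and evidence. The addendum asserts more than 80% power for Aim 1 with 36 patients, and sufficient power with 63, from a table ending at 12 months, while the primary endpoint is at 24.

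At the SAP's effects of 0.667 to 0.714, 63 patients have 24-month power of 0.74 to 0.80 before loss and 0.70 to 0.75 after 10% loss. That is below the 80% target and about the futility level. If crossover cuts the intent-to-treat effect to 0.8 of plan (an assumption), power is 0.51 to 0.56, against 0.62 to 0.68 for the original 82. These figures rest on an unadjusted t-test, near-equal arms and the SDs of Table 2.

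A reader might go on to conclude that 63 patients were too few. The documents do not show this, since covariate adjustment or a larger true effect would raise power. They show only that 80% power at 24 months has not been demonstrated. The text lost from the tables in extraction does not change this: no prose in the addendum mentions a 24-month bootstrap result.

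**What to change.** Amend the SAP addendum of 1/17/13, and one line of 1.6.3:

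1. Limit the statement about 36 patients to the outcomes and intervals that exceed 0.80 (SRS-QOL at 6, 9 and 12 months; ODI at 12 months only), and say that it gives no evidence at 24 months.
2. Replace the sufficiency statement for 63 with 24-month SRS-QOL subscore power at 0.667 to 0.714: 0.74 to 0.80 before loss and 0.70 to 0.75 after 10% loss. Label any crossover dilution as an assumption. Add the expected 95% confidence interval half-width of 0.32 to 0.37 points at SD 0.6 to 0.7.
3. Correct the 70% figure by naming the enrolment goal it refers to; against 82 it is 77%. Correct 0.814 in 1.6.3 to the Table 2 effect size intended.

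The cost is wording only: no extra patients and no change to the analysis. The downside is a less favourable stated power.
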